5.2.13 Inexact Values

In the case where a variable is recorded as “ $> x$ ”, “ $\geq x$ ”, “ $< x$ ” or “ $\leq x$ ”, a value of x will be taken for analysis purposes.

QMD Ref. [REDACTED]	Governing QMD: [REDACTED]
Confidentiality Statement	
This document is the property of [REDACTED] without prior approval from [REDACTED]	and may not be duplicated, copied, altered or removed from company or in compliance with [REDACTED]

		Controlled Quality Management Document	
		Sponsor:	Pitant Therapeutics Inc
		Protocol Number:	PLN-74809-IPF-205
STATISTICAL ANALYSIS PLAN			

5.2.14 Electrocardiogram Data

For electrocardiogram (ECG) data recorded on continuous scales, if replicate (ie, triplicate) values are recorded at a time point, the mean of the replicates rounded to the nearest integer will be used for summarization. For overall interpretation, if more than one value is recorded, the most severe (worst case) of the respective readings will be taken.

Only ECG data for specified visits and time points will be summarized. All ECG data will be presented in listings.

5.2.15 Electrocardiogram Abnormalities

Any QTcF interval (ms) result meeting the following criteria will be identified as an ECG abnormality:

Grade	Abnormality
1	Postbaseline value >450 and ≤ 480 msec
2	Postbaseline value >480 and ≤ 500 msec or postbaseline increase >30 and ≤ 60 msec
3	Postbaseline value >500 msec or postbaseline increase >60 msec
4	Incidence of Torsade de pointes, Ventricular tachycardia, Arrhythmia

In addition, a listing of abnormal QTc results, as identified above, will be provided with the associated grade assigned per the above table. The abnormality will be flagged as 'Confirmed' if the abnormality was observed in 2 consecutive assessments.

5.2.16 Vital Signs

For blood pressure and pulse rate, the orthostatic changes will be calculated as standing minus supine readings.

Temperatures reported in Fahrenheit will be converted to Celsius for reporting using the following formula:

$$\text{Celsius} = (\text{Fahrenheit} - 32)/1.8$$

5.2.17 Pharmacokinetic Parameters

Concentration-time data for total and unbound PLN-74809 will be analysed using noncompartmental methods in [REDACTED]¹ in conjunction with the internet-accessible implementation of [REDACTED]² [REDACTED]

QMD Ref. [REDACTED]	Governing QMD: [REDACTED]
Confidentiality Statement	
This document is the property of [REDACTED] without prior approval from [REDACTED]	and may not be duplicated, copied, altered or removed from company [REDACTED] or in compliance with [REDACTED]
REF: [REDACTED]	

		Controlled Quality Management Document Sponsor: Pliant Therapeutics Inc Protocol Number: PLN-74809-IPF-205
STATISTICAL ANALYSIS PLAN		

During the PK analysis, concentrations below the limit of quantitation (BLQ) up to the time of the first quantifiable concentration will be treated as zero. Embedded (values between 2 quantifiable concentrations) and terminal BLQ concentrations will be treated as “missing”. PK analysis will be performed using actual time relative to dosing. AUC will be calculated using the linear-up log-down method.

The following PK parameters will be calculated for PLN-74809 on Day 1:

- C_{max} : Maximum observed plasma concentration
- AUC_{0-6h} : AUC from the time 0 to 6 hours postdose
- T_{max} : Time to maximum observed plasma concentration
- $C_{max,ub}$: Maximum observed unbound plasma concentration
- $AUC_{0-6h,ub}$: Unbound AUC from the time 0 to 6 hours postdose

PK parameters will be summarized using descriptive statistics.

5.3 Conventions

5.3.1 Medical Coding

Adverse events and medical history will be coded using the Medical Dictionary for Regulatory Activities (MedDRA) Version 26.1. Conditions will be assigned to a system organ class and preferred term based on the Investigator-reported verbatim term.

Any medications taken (other than study drug) will be coded using the World Health Organization Drug Dictionary (WHO Drug), Version B3 Sep 2023. Medications (both prior and concomitant) will be assigned to an Anatomical Therapeutic Chemical (ATC) Level 4 drug classification and preferred name based on the medication name reported on the eCRF.

5.3.2 Data Handling

All clinical data programming will be performed using [REDACTED] [REDACTED] [REDACTED]
 [REDACTED]³ and based on Clinical Data Interchange Standards Consortium (CDISC) data standards.

Study Data Tabulation Model (SDTM) programming will follow SDTM version 1.7 together with SDTM implementation guide 3.3. Analytical Data Model (ADaM) programming will follow ADaM implementation guide 1.1. Specifications for SDTM and ADaM datasets are described in a separate document.

QMD Ref: [REDACTED]		Governing QMD: [REDACTED]
Confidentiality Statement		
This document is the property of [REDACTED] without prior approval from [REDACTED]		and may not be duplicated, copied, altered or removed from company or in compliance with [REDACTED]
REF: [REDACTED]		

		Controlled Quality Management Document
	Sponsor:	Pliant Therapeutics Inc
	Protocol Number:	PLN-74809-IPF-205
STATISTICAL ANALYSIS PLAN		

5.3.3 Summary Statistics

Continuous variables will be summarized using an 8-point summary, the number of nonmissing observations, mean, standard deviation, median, interquartile range (Q1, Q3), minimum, and maximum.

PK concentration-time data and PK parameters will be summarized using a 7-point summary, the number of nonmissing observations (n), arithmetic mean (mean), standard deviation (SD), median, minimum (min), maximum (max), and coefficient of variation (CV%).

Categorical variables will be summarized by presenting the frequency and percent. Percentages will be based on the number of nonmissing observations for the participant population, unless otherwise specified. For each variable, all categories will be shown. Zero frequencies (but not the percent) within a category will be presented.

Incidence of AEs, medical history, and concomitant medications will be reported at the participant level. Participants will only be counted once within each preferred term and system organ class under the highest severity and relationship to study drug. Percentages will be calculated using the number of participants in the treatment group for the safety population.

5.3.4 Decimal Places

For summary statistics, n will be reported as a whole number. Means, medians, and percentiles will be displayed to 1 more decimal place than the data, dispersion statistics (eg, standard deviation) will have 2 more decimal places than the data, and the minimum and maximum will be displayed to the same number of decimal places as reported in the raw data.

Where appropriate, less decimal places may be used on a case-by-case basis as denoted in the table shells.

Percentages will be displayed with 1 decimal place. All data presented in the individual participant listings will be presented as recorded on the eCRF.

5.3.5 P-values

P-values will be displayed to 4 decimal places. P-values <0.0001 will be presented as p<0.0001.

5.3.6 Data Displays

All TFLs will be generated as individual Rich Text Format (.rtf) files. Data summaries and graphical analyses will be reported within Section 14 of the CTR and individual participant data listings within Appendix 16.2 of the CTR.

QMD Ref: [REDACTED]	Governing QMD: [REDACTED]
Confidentiality Statement	
This document is the property of [REDACTED] without prior approval from [REDACTED]	and may not be duplicated, copied, altered or removed from company or in compliance with [REDACTED]
REF: [REDACTED]	

	Controlled Quality Management Document	
	Sponsor:	Pliant Therapeutics Inc
	Protocol Number:	PLN-74809-IPF-205
STATISTICAL ANALYSIS PLAN		

Participant disposition, baseline characteristics, and demographics, will be presented by treatment group (PLN-74809 or placebo) and overall. Other summaries will be presented by treatment group (PLN-74809 or placebo) only.

Treatment group labels will be displayed as follows:

PLN-74809	Placebo	Overall
160 mg (N=XX)	(N=XX)	(N=XX)

Listings will be sorted in the following order: treatment group, participant, parameter, and visit unless otherwise stated. All data will be listed and participants who were not randomized will be displayed after the randomized treatment groups.

5.4 Participant Disposition

The overall total number of participants in the screened population will be summarized. The number of participants randomized will be summarized by treatment group and overall.

Participant disposition will be summarized by treatment group and overall for the safety population, as follows:

- The number of participants in each analysis population (screened, safety, ITT, PK, and PD Populations).
- The number of participants who complete the study drug.
- The number of participants who complete the study.
- The number of participants who early terminated from the study and the reason for early termination.

5.5 Protocol Deviations

Protocol deviations will be summarized by classification (major, minor, and total) and reason by treatment group and overall for the safety population. A listing of protocol deviations will be provided within Appendix 16.2 of the CTR.

5.6 Baseline Comparability

The comparability of treatment groups with respect to participant demographics and baseline characteristics will be assessed in a descriptive manner, but no formal statistical testing will be performed.

Standard continuous or categorical variable summaries will be presented by randomized treatment group for the following variables based on the safety population.

QMD Ref. [REDACTED]		Governing QMD: [REDACTED]
Confidentiality Statement		
This document is the property of [REDACTED] without prior approval from [REDACTED]		and may not be duplicated, copied, altered or removed from company or in compliance with [REDACTED]

		Controlled Quality Management Document
	Sponsor:	Pliant Therapeutics Inc

		STATISTICAL ANALYSIS PLAN
--	--	----------------------------------

Demographic characteristics include:

- Age at Informed Consent (years)
- Sex
- Fertility Status for Women
- Ethnicity
- Race
- Weight at screening (kg)
- Height at screening (cm)
- Body Mass Index at screening (kg/m²)
- Duration of IPF diagnosis (months), defined as the number of months from start date of first date reported for medical history preferred term ‘idiopathic pulmonary fibrosis’ to first dose of study drug
- Participant taking nintedanib or pirfenidone at screening
- Duration of nintedanib or pirfenidone use (months), defined as the number of months from start date of usage of nintedanib or pirfenidone to first dose of study drug
- GAP stage

A listing of demographic characteristics at baseline will be provided.

5.7 Medical History

A summary of previous and ongoing conditions at screening will be presented by randomized treatment group and overall for the safety population. All reported medical history data will be listed. Non-pharmacological procedures will be provided as a separate listing.

5.8 Prior and Concomitant Medications

Separate tabulations will be produced for prior and concomitant medications presented by randomized treatment group and overall for the safety population. Prior medications are defined as all medications started and stopped before the date of the first dose of study drug. Concomitant medications are defined as medications taken on or after the date of the first dose of study drug.

Both prior and concomitant medication verbatim terms (as recorded on the eCRFs) will be mapped to ATC Level 4 and Drug Reference Names using the WHO dictionary (version B3 Mar 2022). Prior and concomitant medications will be summarized using ATC Level 4.

5.9 Exposure to Study Drug

Extent of exposure (number of days of exposure to study drug) will be presented by randomized treatment group for the safety population.

5.10 Treatment Compliance

QMD Ref: [REDACTED]	Governing QMD: [REDACTED]
Confidentiality Statement	
This document is the property of [REDACTED] and may not be duplicated, copied, altered or removed from company without prior approval from [REDACTED] or in compliance with [REDACTED].	

		Controlled Quality Management Document	
		Sponsor:	Pitant Therapeutics Inc
		Protocol Number:	PLN-74809-IPF-205
STATISTICAL ANALYSIS PLAN			

Treatment compliance will be summarized using descriptive statistics based on the classification in Section 5.2.12 by actual treatment group for the safety population.

5.11 Efficacy Analyses

All statistical tests will be performed using a two-tailed 5% overall significance level, unless otherwise stated. All comparisons between treatments will be reported with 95% confidence intervals for the difference.

5.11.1 Primary Endpoint

The primary endpoint is the change from baseline to week 12 in the top quartile mean SUV for the whole lung (average of the right and left lungs).

Whole lung and by lung region top quartile SUVs will be summarized using descriptive statistics by treatment groups and visit for the PD Population.

In addition, an analysis of covariance (ANCOVA) model will be used to summarize the primary endpoint. The model will include terms for baseline top quartile mean SUV and treatment group. The LS means, corresponding SEs, and 95% CI for each treatment group will be obtained from the model. An estimate for the LS mean difference (PLN-74809 vs. placebo), corresponding SE, 95% CI, and *P*-value for each dose group will also be presented.

Example [REDACTED] for ANCOVA model is provided below, [REDACTED] may be added or adjusted for ease of output and interpretation:

[REDACTED]

Where

base	is value at baseline
chg	is change of from baseline
socyn	is the participant's use of standard of care at baseline (Yes or No)
trt	is the dose group

Whole lung and by region metric SUVs will be presented as a box plots by treatment group (side-by-side) with all regions on the same figure.

QMD Ref: [REDACTED]	Governing QMD: [REDACTED]
Confidentiality Statement	
This document is the property of [REDACTED] without prior approval from [REDACTED]	and may not be duplicated, copied, altered or removed from company or in compliance with [REDACTED]
REF: [REDACTED]	

		Controlled Quality Management Document
		Sponsor: Pliant Therapeutics Inc
		Protocol Number: PLN-74809-IPF-205

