^{68}Ga -CBP8, a PET radiotracer that binds specifically to type 1 collagen, has previously been shown to detect and quantify elevated collagen levels in patients with IPF compared to healthy individuals, particularly in the subpleural regions of the lung where fibrosis is known to be prominent (Montesi et al, 2019). Importantly, increased collagen tracer signal was also noted in radiographically normal areas on computerized tomography (CT) prior to architectural distortion, indicating the ^{68}Ga -CBP8 probe may be more sensitive than HRCT in detecting active and/or early fibrosis. Furthermore, ^{68}Ga -CBP8 uptake in mouse lungs has been shown to correlate with levels of fibrosis following injury, with data suggesting that the tracer more readily binds newly formed collagen in active disease than established mature collagen. PLN-74809 consistently, and in a dose-dependent manner, reduced *COL1A1* expression in murine models of bleomycin lung injury and PCLS. These findings suggest that ^{68}Ga -CBP8 may be an effective tool for measuring disease activity (e.g., recently deposited pulmonary collagen levels) and therefore a powerful tool for evaluating efficacy of anti-fibrotic agents such as PLN-74809 in clinical studies. Therefore, in the proposed 12-week study of PLN-74809, the measurement of ^{68}Ga -CBP8 PET ligand will serve two functions; changes over time will provide an exploratory endpoint of both pharmacodynamic (PD) activity and efficacy (reduced collagen levels) of PLN-74809.

To complement the evaluation of antifibrotic effects in the proposed PLN-74809-IPF-205 study, ongoing Phase 2 studies conducted in participants with IPF (PLN-74809-IPF-202) or PSC (PLN-74809-PSC-203) will assess the safety and tolerability of PLN-74809, along with exploratory endpoints relevant to fibrosis. In the PLN-74809-IPF-202 study, exploratory efficacy endpoints will be assessed, including change in forced vital capacity (FVC) and quantitative lung fibrosis (QLF) from baseline following 12 weeks of treatment with PLN-74809. These established (FVC) and exploratory assessments of progressive disease and collagen deposition in IPF will complement the current study, which will be first of its kind to quantify changes in type 1 collagen in the lungs of participants with IPF following 12 weeks of treatment with PLN-74809 using ^{68}Ga -CBP8 PET/ magnetic resonance imaging (MRI) tracer uptake.

2 STUDY OBJECTIVES**2.1 Primary Objective**

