12 PLANNED STATISTICAL METHODS

12.1 General Considerations

This is an exploratory study, with exploratory efficacy and biomarker assessments; as such, no statistical hypotheses are being tested. In general, data will be summarized using statistical summary methods; graphic presentations of data may also be prepared. A statistical analysis plan (SAP), prepared and agreed before final database lock, will describe the analytic approach and methods in more detail.

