12.5 Primary Endpoints

12.5.1 Primary Pharmacodynamic Endpoint

- Quantification of type 1 collagen in the lung following 12 weeks of treatment, as assessed by changes from Baseline in ^{68}Ga -CBP8 PET/MRI tracer uptake patterns.

If a participant elects to withdraw from the study after the 6th week of randomization, an end of participation ^{68}Ga -CBP8 PET/MRI will be offered to the participant to enhance appropriate data capture.

PET/ MRI

PET/MRI scans will be interpreted by American Board of Nuclear Medicine (ABNM)-certified nuclear medicine physicians in an unblinded manner. Lung contours will be generated from baseline and post-treatment PET/MRI. Mean and maximum standardized uptake value (SUV) measurements of contoured lungs will be calculated using MIMS software, by analyzing the uptake values of ^{68}Ga -CBP8 PET/MRI within the lung, and by comparing values from the baseline and post-treatment scans. Numerical and graphical results will be presented by dose.

In addition, relationships between PK and type 1 collagen deposition, as well as between MRI and PET imaging, may be evaluated in an exploratory fashion and presented in a graphical manner (see [Section 12.7.1](#)).

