5.2.4 Standardized Uptake Values

Standardized uptake values (SUVs) will be quantified, using MIMs software as specified in the protocol, for each lung (left and right) and by 6 regions (lower subpleural, lower central, middle subpleural, middle central, upper subpleural, and upper central) as well as whole lung, by the Imaging laboratory from the PET scans. Multiple SUV parameters will be provided for each region. The following parameters will be provided for each region, each lung, and for the whole lung:

- SUVmean: mean of the SUVs for each region in each lung
- SUVmax: maximum of the SUVs for each region in each lung
- SUVtopquartile: mean of the SUVs within the top quartile of each region in each lung

QMD Ref: [REDACTED]	Governing QMD: [REDACTED]
Confidentiality Statement	
This document is the property of [REDACTED] without prior approval from [REDACTED]	and may not be duplicated, copied, altered or removed from company or in compliance with [REDACTED]

		Controlled Quality Management Document Sponsor: Pliant Therapeutics Inc Protocol Number: PLN-74809-IPF-205
STATISTICAL ANALYSIS PLAN		

The mean of both lungs will be constructed as follows:

Region SUV metric = (left region SUV metric + right region SUV metric)/2

Whole lung SUV metric = (left whole lung SUV metric + right whole lung SUV metric)/2

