5.11.3.4 Relationships Between Endpoints

The Spearman correlation will be utilized to assess the correlations between the following endpoints in each treatment group. The Spearman correlation coefficient will be presented with the *P*-value for each pair of endpoints.

- By region SUV to by region SUV using change from baseline in top quartile SUV
- Change from baseline in whole lung top quartile SUV, change from baseline in PRO-C3, change from baseline in CTX-III_HP, change from baseline in ITGB6, change from baseline in FVC (mL), change from baseline in FVC percent predicted (%), and observed PLN-74809 Week 12 pre-dose concentration (total and unbound).

Sample [REDACTED] for Spearman correlation:

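### Does the SAP leave the primary metric, whole-lung top-quartile SUV, open to two different calculations?

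*SAP*

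**What the plan says.** Protocol 12.5.1 describes the endpoint as change in tracer uptake patterns and names two summaries: "Mean and maximum standardized uptake value (SUV) measurements of contoured lungs will be calculated using MIMS software". It makes neither of them primary. Protocol 12.1 says the study tests no hypotheses and that the SAP "will describe the analytic approach and methods in more detail".

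SAP 2.2.1 lists whole-lung SUV as the primary endpoint without naming a parameter. SAP 5.11.1 names it: "The primary endpoint is the change from baseline to week 12 in the top quartile mean SUV for the whole lung", with the right and left lungs averaged. SAP 5.11.2.1 places SUVmean and SUVmax under exploratory efficacy and analyses them in the same way.

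The derivation is in SAP 5.2.4. On the levels supplied it says: "The following parameters will be provided for each region, each lung, and for the whole lung". On the metric it says: "SUVtopquartile: mean of the SUVs within the top quartile of each region in each lung". On combining the lungs it says: "Whole lung SUV metric = (left whole lung SUV metric + right whole lung SUV metric)/2".

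SAP Section 9, as supplied, records the move to whole lung as a clarification and does not mention the top-quartile metric.

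**The concern.** The bullet that defines the metric speaks of regions, while the primary endpoint is a whole-lung value. The left and right whole-lung values in the averaging formula are not separately defined. Two candidates come to mind for a single lung:

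- **A:** pool all SUVs in the lung and take the mean of the highest 25%.
- **B:** take the top-quartile mean in each of the six regions and average those over the lung.

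A follows the hottest tissue wherever it lies. B gives every region a share and so moves more like a whole-lung mean. The protocol's rationale (section 1.2) expects raised tracer signal "particularly in the subpleural regions of the lung where fibrosis is known to be prominent", so uneven uptake is the trial's own premise, and uneven uptake is what separates A from B. The choice would feed the LS mean difference, confidence interval and P-value in SAP 5.11.1, and the correlations in SAP 5.11.3.4, which start from "Change from baseline in whole lung top quartile SUV, change from baseline in PRO-C3".

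The record of the choice is also thin. A metric absent from the protocol became primary, and Section 9, which gives reasons for the biomarker changes and for dropping end-of-study FVC, does not list it.

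**Working it through.** **1. What the text fixes.** SAP 5.2.4 lists each lung, the six regions and the whole lung as levels at which the imaging laboratory quantifies SUV. The lung is thus a measured level, not one assembled later from regions. The section writes out two averaging formulas, one for regions and one for whole lung. Both combine left with right. Neither combines six regions into one lung.

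Reading B needs that missing step and also a weighting rule (equal or by volume). Reading A needs only that the lung be treated as its own region of interest, which matches Protocol 12.5.1, where SUV is measured on contoured lungs.

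**2. The same wording on the sister metrics.** SUVmean and SUVmax carry the same by-region phrase. Read literally in the manner of B, the whole-lung SUVmax of each lung would be an average of six regional maxima, which is no longer a maximum. The phrase is loose drafting shared by all three bullets and is weak evidence for a second definition.

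**3. Who computes it.** SAP 5.2 says that, unless stated otherwise, variables derived in the source data are not recalculated. The trial statistician averages the two lung values delivered and does not choose between A and B.

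**4. How far apart A and B could be.** The documents give no regional uptake, voxel spread or effect size for SUV, so there is no figure of the plan's to reproduce. All inputs here are assumed: three subpleural and three central regions of equal volume, central mean 1, subpleural mean r, voxel SUV normal with SD = CV x regional mean.

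- *B.* Each region's top-quartile mean is its mean times (1 + 1.271 x CV). That factor cancels in a percent change. A 20% subpleural-only fall gives -20% x r/(r+1); a central-only fall gives -20% x 1/(r+1). At r = 1.5: -20% x 0.6 = -12.0% and -20% x 0.4 = -8.0%.
- *A.* Find the cut-off c above which 25% of the pooled voxels lie, take the mean above c before and after the change, and form the ratio.

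| r | CV | Subpleural-only fall, A / B | Central-only fall, A / B |
|---|---|---|---|
| 1.2 | 0.2 | -13.1% / -10.9% | -1.7% / -9.1% |
| 1.2 | 0.3 | -12.4% / -10.9% | -3.3% / -9.1% |
| 1.2 | 0.7 | -11.6% / -10.9% | -6.1% / -9.1% |
| 1.5 | 0.2 | -18.6% / -12.0% | 0.0% / -8.0% |
| 1.5 | 0.3 | -17.2% / -12.0% | -0.5% / -8.0% |
| 1.5 | 0.7 | -14.8% / -12.0% | -3.3% / -8.0% |
| 2.0 | 0.2 | -20.0% / -13.3% | 0.0% / -6.7% |
| 2.0 | 0.3 | -19.8% / -13.3% | 0.0% / -6.7% |
| 2.0 | 0.7 | -17.8% / -13.3% | -1.0% / -6.7% |

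A uniform 20% fall gives -20.0% under both readings in every row. For a subpleural-only fall the gap runs from 0.7 points (11.6 - 10.9) to 6.7 points (20.0 - 13.3), depending wholly on the assumed r and CV.

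**5. Effect on the test.** Simulated 8 versus 4 trials used the ANCOVA with baseline and treatment (12 - 3 = 9 residual degrees of freedom), r = 1.5, CV 0.25 and assumed log-scale change SDs of 0.06 to 0.10 (regional) and 0.08 to 0.15 (person). A and B fell on opposite sides of P = 0.05 in 14.0% to 25.1% of trials with a subpleural-only effect, 10.0% to 25.8% with a central-only effect, 3.0% to 8.2% with a uniform effect and 2.4% to 3.4% with none. Under no effect, each reading alone kept its false-positive rate at about 5%.

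**The case for a change.** The strongest case for a change is that stating which levels will be delivered is not the same as saying how each is formed. No sentence in either document says that a lung's top quartile is cut over all its SUVs. If the laboratory worked by B, nobody reading the SAP would know, and with uneven uptake the estimate could differ by several points. One sentence would settle it. A dated reason for choosing the metric would also help readers judge it, the more so because Protocol 12.5.1 has the scans read unblinded.

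Part of this stands. The lung-level wording is incomplete, SAP 2.2.1 could name the parameter, and Section 9 as supplied omits it. But the sentence asked for would only write down whichever definition is already meant; it would not replace the method with a better one. The Radiology Manual, which Protocol 7.10.1 cites for imaging instructions, may already hold it; that cannot be checked here.

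On the record of the choice, Protocol 12.1 leaves analytic detail to the SAP, SAP Section 5 requires approval before database lock, and the SAP Introduction sends changes from the protocol's planned analysis to the Clinical Trial Report. The protocol never ranked mean above maximum SUV, and both are still reported with the same model. SAP 5.11.1 also reports top-quartile SUV by region, with box plots of the whole lung and all regions on one figure, so a focal change that would separate A from B would be visible. Unblinded reading is a separate matter that a definition would not touch.

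**Conclusion.** No change to the plan follows. This is a gap that analysts fill sensibly. The natural reading of SAP 5.2.4 and 5.11.1 takes the top quartile over each lung and averages left and right. The rival reading needs a combining rule that the SAP does not contain, and the values come ready-made from the imaging laboratory.

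The possible size, 0.7 to 6.7 percentage points for a 20% subpleural-only fall and zero for a uniform one, rests entirely on assumed ratios of 1.2 to 2.0, voxel CVs of 0.2 to 0.7, equal regional volumes and normal voxel values. The real size cannot be found from the documents. Neither reading is shown to be biased. Disagreement about P < 0.05 also carries limited weight in a study of about 12 participants whose protocol disclaims hypothesis testing, although SAP 5.11.1 does plan a P-value.

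The unnamed parameter in SAP 2.2.1 and the missing Section 9 entry are points of record-keeping. The conclusion would be different if the laboratory's delivered lung values turned out to be built from regional top quartiles.
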